11.4.4 PROVISIONS FOR INJURY

If a subject experiences an injury that is directly related to this study, the event will be followed up until its resolution. Nationwide Children's Hospital will provide medical treatment reasonably necessary for such injury or illness at no cost to the subject or his insurance company for [REDACTED]. In order for The Research Institute at Nationwide Children's Hospital to pay for these medical expenses the illness or injury must not be related to subject's underlying medical condition and subject must have followed the study directions.

If research subject seeks care for a research related injury or illness from a medical provider other than Nationwide Children's Hospital, then The Research Institute at Nationwide Children's Hospital will [REDACTED]

such injury or illness directly resulting from the study. Any claim for reimbursement must be supported by documentation such as a bill or invoice from a medical provider. In order for The Research Institute at Nationwide Children's Hospital to pay for these medical expenses the research subject's illness or injury must not be related to his/her underlying medical condition and research subject must have followed the study directions.

The Research Institute at Nationwide Children's Hospital's reimbursement for injury or illness as a result of research subject's participation in the study does not include any payment for lost wages, lost time, emotional distress or pain. This does not mean that the research subject gives up any of his legal rights to seek compensation for his illness or injury.

11.5 POTENTIAL BENEFITS OF THE PROPOSED RESEARCH TO THE SUBJECTS AND OTHERS

This is primarily a safety study of transfer of scAAVrh74.tMCK.hSGCA with the potential to increase lower limbs muscle strength. If muscle strength is increased in knee extension/flexor it has the potential to make a difference for subjects in prolonging ambulation and preventing falls.

11.6 INCLUSION OF MINORITIES IN CLINICAL RESEARCH

11.6.1 SELECTION CRITERIA

Seven LGMD2D subjects will be enrolled in this trial. Eligibility criteria will include subjects with proven alpha-sarcoglycan deficiency by muscle biopsy or DNA testing. Participants will encompass any ethnic or racial background.

11.6.2 TARGETED/PLANNED ENROLLMENT

The number of subjects enrolled from each ethnic group will mirror that seen in the clinic population.

Table 6.5. Local distribution of the disease (percent)

Gender	American Indian Alaskan Native	Asian or Pacific Islander	Hispanic	Black, Non-Hispanic	White, Non-Hispanic	Total
Female	0	0	10	0	30	40
Male	0	0	40	0	20	60
Total	0	0	50	0	50	100

11.6.3 PROPOSED DATES OF ENROLLMENT AND RECRUITMENT

We anticipate beginning enrollment in January 2014, with completion of enrollment December 2017. This protocol is listed in the Clinical Trials Data Bank of the NIH.

12.0 DATA AND SAFETY MONITORING PLAN

12.1 THE DATA SAFETY MONITORING BOARD

The Data and Safety Monitoring Board (DSMB) will act in an advisory capacity to review participant safety and study progress for the “Phase I/IIa gene transfer clinical trial for LGMD2D (alpha-sarcoglycan deficiency) using scAAVrh74.tMCK.hSGCA” trial.

Responsibilities of the DSMB are to:

- review the research protocol, informed consent documents and plans for data and safety monitoring;
- evaluate the progress of the trial, including periodic assessments of data quality and timeliness, participant recruitment, accrual and retention, participant risk versus benefit, trial site performance, and other factors that can affect study outcome;
- consider factors external to the study when relevant information becomes available, such as scientific or therapeutic developments that may have an impact on participant safety or the ethics of the trial;
- review study performance, make recommendations and assist in the resolution of problems reported by the Principal Investigator;
- protect the safety of the study participants;

- review safety data to determine whether to recommend dose escalation;
- ensure the confidentiality of the trial data and the results of monitoring; and,
- assist by commenting on any problems with study conduct, enrollment, and sample size and/or data collection.

DSMB Reporting and Meetings

Reports describing the status of the study will be prepared by the Principal Investigator's staff and sent to the DSMB through KAI at the end of each cohort, or at the DSMB's request.

An initial meeting (either by teleconference, webcast, or paper report) with the DSMB is scheduled prior to study initiation and at the DSMB's request. Reports will be submitted at least 2 weeks prior to a scheduled meeting for review by the DSMB.

Reports will include the following:

- A brief narrative of the study status, including the target enrollment, current and projected time to completing enrollment. Any significant events and/or difficulties should be briefly described in this narrative.
- A brief narrative for each participant describing gender, age, race and ethnicity and other relevant demographic characteristics. The narrative for each participant should briefly describe his/her study status (i.e., dose level, visit number, adverse event information);

- A timeline outlining the study progress relative to visit number for each participant, as well as time points for each SAE/Dose Limiting Toxicity. A total for Adverse Events (AEs) for each participant should be included.
- A summary of AEs by severity levels;
- A listing of AE details grouped by participant;
- A listing of SAE details grouped by participant;
- A listing of deaths
- A summary of clinically significant laboratory test results
- A listing of protocol deviations

Stopping/Discontinuation Rules

An independent Data Safety Monitoring Board (DSMB) has been approved by the study's sponsor (National Institute of Health). Safety data will be monitored on a continual basis throughout the trial. The DSMB can recommend early termination of the trial for reasons of safety. Study enrollment will be halted and discussed with the DSMB by the investigators when any subject experiences a Grade 3 or higher adverse event toxicity that is possibly, probably, or definitely related to the study drug. This will include any subject death, important clinical laboratory finding, or any severe local complication in the injected area related to administration of the study agent. If after review by the DSMB, IRB, IBCSC, NIH-OBA and FDA,

the decision is made to continue, the study will proceed according to Dose Escalation plan.

MEMBERSHIP

The DSMB membership consists of persons completely independent of the investigator who have no financial, scientific, or other conflicts of interest with the trial. Current or past collaborators or associates of [REDACTED] must note any conflict of interest before their eligibility to serve on the DSMB is approved.

The DSMB will include experts in or representatives of the fields of:

- Neurology and Neuromuscular Diseases
- Immunology
- Gene Therapy
- Muscular Dystrophy Clinical Care
- Clinical Research and Clinical Trials

Conflict of Interest

Individuals invited to serve on the DSMB as either voting or non-voting members must disclose any potential conflicts of interest, whether real or perceived. Conflicts of interest can include professional, proprietary, and miscellaneous interests as described in the NIH Grant Policy Statement and 45 CFR Part 94. Potential conflicts that develop during a member's tenure on a DSMB must also be disclosed. Written documentation attesting to an absence of conflict of interest is required annually.

13.0 CLINICAL MONITORING OF THE STUDY

The study will be monitored in compliance with the relevant parts of 21 CFR and according to the ICH GCP Guidelines.

The procedures outlined in the protocol and case report forms will be carefully reviewed by the PI and staff prior to study initiation to ensure appropriate interpretation and implementation. No deviations from the protocol shall be made except in emergency situations where alternative treatment is necessary for the protection, proper care and well-being of subjects.

Amendments will be submitted to the Nationwide Children's Hospital IRB for their review and approval prior to implementation. When an amendment to a protocol substantially alters the study design or increases potential risk to the study subject, the Informed Consent form will be revised and if applicable, subject's consent to continue participation will again be obtained.

13.1 DATA MANAGEMENT AND STUDY FORMS

All data and observations will be documented on electronic Case Report Forms (CRF) by source documentation using the Open Clinica Electronic Data Capture designed for the study. A Safety Monitor will have access to the data to monitor adherence to the protocol and to applicable FDA regulations, and the maintenance of adequate and accurate clinical records. An electronic Case Report Form will be completed for every subject that was registered for participation in the study. The Case Report Form will be reviewed in detail. Case Report Forms will be completed as information becomes available.

Case Report Forms will be reviewed in detail by the Safety Monitor in a regular basis for which the Safety Monitor will have access to subject medical records, laboratory data, and other source documentation. Safety monitor will make a decision as to the data acceptability. If errors or omissions are found in the course of a data audit, or if clarification of data is required, the electronic Case Report Form(s) in question will be corrected by the PI or his designee. Data Resolution may be generated on omissions or clarifications, to be completed, electronically signed and dated, and maintained as a part of the eCRF. The PI will sign and accept the indicated electronic Case Report Form. This signature will indicate that thorough inspection of the data therein has been made and will thereby certify the contents of the form.

In collaboration with the study team, the Research Informatics Core designed a data collection system (Open Clinica) for managing the clinical trial. A web-based database was created and it will be managed by authorized users. CRFs will be transcribed to this web-based database. Data will be extracted from source documents (lab reports, echo reports...) and transferred to the

database as well. All source documents will be kept in the Subject Research Chart. The secured portal will feature view and edit capability with field validations for quality controls, change history attribute and reporting.

An outside contracted monitor of the study called a "CRO" will also monitor the study on a regular basis to make sure the study is conducted in compliance with all regulatory aspects of the protocol.

14.0 AGENT ACCOUNTABILITY

14.1 HANDLING OF INVESTIGATIONAL AGENT

"Investigator shall take adequate precautions, including storage of the investigational drug in a securely locked cabinet or other securely locked, substantially constructed enclosure, access to which is limited, to prevent theft or diversion of the substance into illegal channels of distribution." (Code of Federal Regulations, Title 21, Part 312 .69).

All materials used for injection, including sterile drapes, needles and syringes in contact with the vector will be sealed in leak proof primary and secondary containers. To ensure the highest safety precautions, all waste will be double bagged in autoclave bag bearing the biohazard symbol and sealed with autoclave tape bearing name and room number. The bag will then be autoclaved and disposed of in a biohazard waste container with name and room number.

All surfaces will be wiped with 10% bleach with a 70% ethanol rinse. Immediate decontamination procedures are performed whenever overt spills, splashes or other contaminating events occur. All absorbent material is placed onto a blue absorbent pad and transferred into a properly labeled biohazard bag.

Spills will be covered with absorbent paper towels and freshly prepared 10% bleach will be applied starting at the perimeter and working towards the center. At least 30 minutes will be allowed after contact time before clean up. In case of large spills, IBCSC and Environmental Services will be notified immediately.

If an accidental exposure occurs (such as accidental needle stick), the exposure site will be washed with soap and water.

Spills and accidents resulting in potential exposure of AAV to individuals will be reported to [REDACTED] IBCSC, and the Employee Health Services within 24 hours. Medical evaluations, surveillance, and treatment will be provided by the EHS. All information concerning the incident is to be documented and submitted to [REDACTED], IBCSC, and the EHS.

Only authorized personnel will be permitted in the surgery room during injection process. During the injection all personnel will be required to wear lab coat, gloves, respiratory mask, glasses, and toe covered shoes. All study staff must have documentation of taking the laboratory training safety module provided by the IBCSC. The link to the online training is the following:

<http://rex/Training/Pages/IBCSC%20Training.aspx>

14.2 DISPOSITION OF STUDY AGENT

"Investigator is required to maintain adequate records of the disposition of the drug, including dates, quantity, and use by subjects. If the investigation is terminated, suspended, discontinued, or completed, the investigator shall return the unused supplies to the sponsor, or otherwise provide for disposition of the unused supplies (as authorized by the sponsor)." (Code of Federal Regulations, Title 21, Part 312 .62, Section a).

12. To not make any changes in the research without IRB approval, except where necessary to eliminate apparent immediate hazards to human subjects;
13. To comply with all other requirements regarding the obligations of clinical investigators and all other pertinent requirements in 21 CFR 312.

Nationwide Children's Hospital

Nationwide Children's Hospital is one of the nation's most progressive and sophisticated health care institutions. A multitude of comprehensive programs, integrating medical and surgical sub-specialties, is the core for tertiary care provided at Children's Hospital. Services are integrated between the inpatient and outpatient areas to enable a full continuum of subject care.

The Nationwide Children's Hospital's services for this study are

- Providing research beds and hospital facilities for the inpatient phase of the research study

- Subject care services and nursing support during the inpatient phase of the research study

Clinical Study Center/ Outpatient Neuromuscular Clinic

- Providing facilities for the follow up visits after gene transfer.

DLT	Dose limiting toxicity
eCRF	Electronic case report form
eDISH	Evaluation of Drug-Induced Serious Hepatotoxicity
FAS	Full analysis set
FDA	Food and drug administration
LGMD2D	Limb-girdle muscular dystrophy type 2D
MedDRA	Medical dictionary for regulatory activities
MTD	Maximum tolerated dose
PBMC	Peripheral blood mononuclear cells
PT	Preferred term
SAE	Serious adverse event
6MWT	Six-minute walk test
SAP	Statistical analysis plan
SAS	Statistical analysis system
SD	Standard deviation
SMQs	Standardized MedDRA Queries
SOC	System organ class
TEAE	Treatment-emergent adverse event
TESAE	Treatment-emergent serious adverse event
ULN	Upper limit of normal
vg	Vector genomes

Sponsor Name: Sarepta Therapeutics, Inc.

Sponsor Protocol ID: 9004-101 Covance Study ID: 000000209191

1. Source Documents

The Statistical Analysis Plan (SAP) was written based on the following documentation:

Document	Date	Version
Protocol	10Feb2017	11.0

2. Protocol Details

2.1 Study Objectives

2.1.1 Primary Objective

 Determine the safety of intravascular administration of self-complementary scAAVrh74.tMCK.hSGCA delivered via a major lower limb artery targeting all of the lower limb muscles of Limb-girdle muscular dystrophy type 2D (LGMD2D) (alpha-sarcoglycan [a-SG] deficient) subjects

2.1.2 Secondary Objectives

Assessment of the efficacy of the same vector measured by:

• The distance walked in 6 minutes

2.2 Overall Study Design

This study is a dose escalation, Phase I/IIa study of self-complementary scAAVrh74.tMCK.hSGCA vector and transgene to LGMD2D (a-SG deficient) subjects delivered via a major lower limb artery of each leg sequentially by isolated limb infusion.

Three cohorts (Cohorts 1A, 1B, and 2) will undergo gene transfer in a standard three-six dose escalation scheme to establish maximum tolerated dose (MTD) using toxicity. One adult wheelchair-dependent patient will be enrolled in Cohort 1A, three subjects will be enrolled in Cohort 1B, and three subjects will be enrolled in Cohort 2. The first cohort (1A) will receive a vector dose of $1 \times 10^{12} \, \text{vg/kg}$ (optimized weight to height) in a single limb with delivery to the whole limb. This same dose will be

delivered to both limbs in Cohort 1B. Cohort 2 will receive a total dose of 3 x 10^{12} vg/kg per limb delivered to both lower extremities. The vector will be infused into an indwelling vascular sheath placed in the femoral artery. This will be a one-time vector infusion to an isolated limb with an approximately 10-minute dwell time.

Short-term safety over a two-year period will be evaluated. Subjects will be tested at baseline, infusion visit (days 0-1), and return for follow up visits on days 2, 7, 14, 30, 60, 90, and 180 and at months 9 (physical therapy only), 12, 18, and 24.

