1.0 PROTOCOL SYNOPSIS

Title	Phase I/IIa gene transfer clinical trial for LGMD2D (alpha-sarcoglycan deficiency) using scAAVrh74.tMCK.hSGCA.
Study Number	N = 7: [Low dose single leg (n=1) and bilareral (n =3) and High dose bilateral (n=3)]
Clinical Study Phase	Phase I/IIa trial
Number of Centers	Single site (Nationwide Children’s Hospital)
Study Objectives	Primary objective is safety
Study Design	Dose escalation study of self-complementary (sc) AAVrh74.tMCK.hSGCA delivered to single leg (low dose n=1) and bilaterally (n=6) via a major lower limb artery to the whole lower limb of LGMD2D (alpha-SG deficient) subjects.

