6.3 PROTOCOL FOR GENE TRANSFER

The clinical trial is a dose escalation study of scAAVrh74.tMCK.hSGCA delivered by isolated limb infusion via a sidearm sheath (REF CP-08403; Manufacturer: Arrow) placed percutaneously in the femoral artery and allowed to circulate through the limb vasculature. Prior to vector delivery the limb circulation is isolated from the central circulation by the careful placement of occlusive balloon catheters (Tyshak II Balloon Dilatation Catheter; Manufacturer: B. Braun Intervention Systems Inc., and NuMED, Inc.) one placed through the arterial sheath in a cephalad direction positioned above the profunda artery and a second occlusive balloon positioned via a similarly placed sidearm sheath placed in the femoral vein. Following placement of the arterial and venous sidearm sheaths and before the insertion of the occlusive balloons the subject is anticoagulated with unfractionated heparin. The balloons are then positioned under flouroscopy guidance and inflated to create stasis in the limb during the infusion procedure. [REDACTED]

[REDACTED]

[REDACTED]

[REDACTED]

[REDACTED]

[REDACTED]

[REDACTED]

[REDACTED]

For the subjects in cohort 1A the arterial and venous sheaths will be placed and procedure will continue as described above. For the subjects in cohorts 1B and 2—both limbs—the vascular sheaths will be placed on both sides (left and right) and the the subject will be anticoagulated and the occlusive balloon catheters positioned one side and the subject dosed. Upon completion of dosing of the first extremity, the other will be done. Three cohorts will undergo gene transfer in a dose escalation scheme to establish maximum tolerated dose (MTD) using toxicity. Cohort 1A (n=1) will receive a vector dose of 1×10^{12} vg/kg in a single lower extremity. In Cohort 1B (n=3), three subjects will receive the same vector dose per limb delivered bilaterally to both lower extremities for a total dose of 2×10^{12} vg/kg. This will be a one-time vector infusion as described above. Subjects in Cohort 2 (n=3) will receive 3×10^{12} vg/kg vector dose per extremity (6×10^{12} vg/kg total dose) delivered according to the identical protocol.

[REDACTED]

[REDACTED]

[REDACTED]

[REDACTED]

[REDACTED]

[REDACTED]

[REDACTED]

[REDACTED]

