6.6 OUTCOME MEASURES

The study is a Phase I/IIa clinical trial inclusive of safety and efficacy outcome measures

- A. Safety is the primary outcome for this clinical gene transfer trial. Stopping criteria are based on development of unacceptable toxicity defined as the occurrence of any one Grade III or higher treatment-related toxicities, or two or more Grade II treatment-related toxicities.

B. Efficacy outcome measures include:

i. Strength and functional testing will be performed at baseline and at days 60, 90, 180, and at 9, 12, 18, and 24 months. This will include the 6MWT distance as the primary functional variable. [REDACTED]

[REDACTED]

[REDACTED]

[REDACTED]

[REDACTED] Pre- and post-treatment strength, distance, and time will be evaluated by using paired t-tests.

[REDACTED]

[REDACTED]

[REDACTED]

[REDACTED]

[REDACTED]

[REDACTED]

[REDACTED]

[REDACTED]

[REDACTED]

[REDACTED]

[REDACTED]

[REDACTED]

iii. Immune response will be assessed by IFN- γ ELISpots to alpha-sarcoglycan and AAV capsid. A rise in IFN- γ of 50 spot forming colonies per one million PBMCs towards virus or transgene will be considered significant. An additional measure of immune response will be the binding antibody assay to AAV.

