7.5 STOPPING/DISCONTINUATION RULES

An independent Data Safety Monitoring Board (DSMB) will be established by the sponsoring agency including a safety monitor for the study. Safety data will be monitored on a continual basis throughout the trial. The DSMB can recommend early termination of the trial for reasons of safety. Study enrollment will be halted by the investigators when any subject experiences a Grade 3, or higher adverse event toxicity that is possibly, probably, or definitely related to the study drug. This will include:

- Grade 3
 - Severe or medically significant but not immediately life-threatening;
 - Hospitalization or prolongation of hospitalization indicated;
 - Disabling; limiting self care ADL**.
- Grade 4
 - Life-threatening consequences;
 - Urgent intervention indicated.
- Grade 5
 - Death related to AE.

Activities of Daily Living (ADL)

*Instrumental ADL refer to preparing meals, shopping for groceries or clothes, using the telephone, managing money, etc.

****Self care ADL refer to bathing, dressing and undressing, feeding self, using the toilet, taking medications, and not bedridden.**

If after review by the DSMB the decision is made to continue, the study will proceed according to Section 6.2.7.6 (Dose escalation) of this protocol.

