7.6 DOSE ESCALATION

There will be 4 weeks between dosing of subjects within a cohort. For the first cohort, the allowance of four weeks between dosing of subjects provides time for safety review from five time points (days 1, 2, 7, 14 and 30) prior to dosing of the next subject and time for review of the safety analysis of all the subjects within a cohort by the investigators and the DSMB.

This timeline will also provide time for review of any clinically significant improvement based on the 6MWT data. [REDACTED]

[REDACTED]

The investigators will confer with the IRB, DSMB, and FDA/CBER on all grade – 3 or higher adverse events that are possibly, probably, or definitely related to the study agent before continuing enrollment. Based on the outcome of the safety and efficacy analysis at the end of each cohort decisions will be made to proceed with dose escalation for the following cohort.

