2.3 Sample Size and Power

Seven LGMD2D subjects with a-SG deficiency by muscle biopsy or DNA testing will be enrolled at Nationwide Children's Hospital for the gene transfer study:

- Cohort 1A: One (n=1) adult LGMD2D wheelchair-dependent subject will receive single-limb perfusion at the low dose: 1x10¹² vg/kg per lower extremity.
- Cohort 1B: Three (n=3) LGMD2D subjects will receive bilateral whole limb perfusion at the low dose: 1x10¹² vg/kg per lower extremity.
- Cohort 2: Three (n=3) LGMD2D subjects will receive bilateral whole limb perfusion at the high dose: 3x10¹² vg/kg per lower extremity.

If safety data is satisfactory at low dose in single limb (Cohort 1A), the same dose will be used for bilateral lower limb infusion (Cohort 1B). With satisfactory safety data, high dose will be used for bilateral lower limb infusion (Cohort 2).

3. Efficacy and Safety Endpoints

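### The three-six label and the MTD purpose in SAP 2.2 do not fit cohorts fixed at 1 + 3 + 3, and the DLT, stopping and grade wordings need reconciling

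*SAP*

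**What the plan says.** **Label.** SAP 2.2 says that the three cohorts will undergo gene transfer "in a standard three-six dose escalation scheme to establish maximum tolerated dose (MTD) using toxicity". Protocol 2.0 has the same words. Protocol 6.3 drops the three-six label but keeps the purpose: "Three cohorts will undergo gene transfer in a dose escalation scheme to establish maximum tolerated dose (MTD) using toxicity".

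**Size.** In SAP 2.2 and Protocol 2.0 the next sentence sets the cohorts at one, three and three. The Protocol synopsis gives N = 7, made up of "Low dose single leg (n=1) and bilareral (n =3) and High dose bilateral (n=3". Protocol 3.0 and SAP 2.3 also give seven.

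**Escalation.** SAP 2.3: "With satisfactory safety data, high dose will be used for bilateral lower limb infusion (Cohort 2". Protocol 7.6: "Based on the outcome of the safety and efficacy analysis at the end of each cohort decisions will be made". Under Protocol 12.1 the DSMB is to "review safety data to determine whether to recommend dose escalation".

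**Halting and stopping.** Protocol 7.5: "Study enrollment will be halted by the investigators when any subject experiences a Grade 3, or higher adverse event toxicity that is" at least possibly related to the product. Protocol 7.4 and 12.1 use the same trigger. Protocol 6.6 defines unacceptable toxicity as "any one Grade III or higher treatment-related toxicities, or two or more Grade II treatment-related toxicities".

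**DLT.** Protocol 7.4 defines a DLT as any adverse event at least possibly related to the agent and adds that this includes any Grade 3 event. Later in the same section it admits only events that needed treatment.

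**SAP analyses.** The SAP lists DLT and MTD as abbreviations. Its visible safety analyses contain no DLT tabulation and no MTD determination.

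**The concern.** A reader who sees a standard escalation scheme with an MTD purpose will expect three things: a size that can grow at a dose level, a rule for when it grows, and a rule that names the MTD. The size is fixed, and neither rule is visible. The SAP therefore states a design property that the visible plan does not have.

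The risk is one of interpretation. MTD is not an objective (Protocol 4.1, SAP 2.1) or an endpoint, so no planned result is lost. But the label invites the report, or its readers, to treat the high dose in three subjects as at or below an established MTD.

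The DLT, stopping and grade wordings are a separate problem. Protocol 8.3 ties 48-hour reporting to DLTs, and Protocol 12.1 puts DLTs on the DSMB timeline. Which events count depends on which sentence is applied.

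**Working it through.** **1. The plan's own figure.** Cohort 1A + 1B + 2 = 1 + 3 + 3 = 7, as stated. No alpha, power or target toxicity rate is visible, so there is nothing else to reproduce.

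**2. Room for expansion.** Assume that three-six means three subjects at a dose, expandable to six.

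- No bilateral cohort expands: 1 + 3 + 3 = 7
- One expands: 1 + 6 + 3 = 10
- Both expand: 1 + 6 + 6 = 13

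Counting the Cohort 1A subject toward the low per-limb dose does not help. That gives 1 + 3 = 4 at the low dose, and filling it to six gives 6 + 3 = 9, or 6 + 6 = 12 if both levels fill. The fixed seven fits only the case in which nothing expands.

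**3. Rules in visible text.**

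| Question | Visible answer |
|---|---|
| When is enrolment halted? | One related Grade 3+ event (Protocol 7.4, 7.5, 12.1); Protocol 6.6 adds two or more related Grade II |
| When does the dose go up? | Satisfactory safety data, decision at the end of each cohort, DSMB advice |
| When does a cohort go from three to six? | Nothing visible |
| How is the MTD declared? | Nothing visible |

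Redactions fall in the synopsis statistics row, Protocol 6.7 and Protocol 7.6, where such rules could sit.

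**4. How often the gap would matter.** The documents give no expected rate, so per-subject rates p of 10% to 50% are assumed. For three subjects:

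- P(at least one event) = 1 − (1 − p)³
- P(exactly one event) = 3p(1 − p)², the result that calls for expansion under the usual three-to-six convention (also assumed)

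| p | At least one of 3 | Exactly one of 3 |
|---|---|---|
| 10% | 27.1% | 24.3% |
| 20% | 48.8% | 38.4% |
| 30% | 65.7% | 44.1% |
| 40% | 78.4% | 43.2% |
| 50% | 87.5% | 37.5% |

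If the events are related Grade 3+ events, the middle column is the chance that a bilateral cohort halts and goes to review. That is the halt working as written. The last column is the chance of meeting a result for which the label implies an expansion that N = 7 does not allow.

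**5. What a clean cohort shows.** The exact two-sided 95% upper limit for 0/n is 1 − 0.025^(1/n). For 0/3 it is 1 − 0.025^(1/3) = 0.708. For 0/6 it would be 1 − 0.025^(1/6) = 0.459. This width comes from the sample size, not from the label. It bears only on how a statement of tolerability is worded.

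**6. The wordings side by side.**

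- *Stopping.* Two related Grade II toxicities meet the criterion in Protocol 6.6 and do not meet the halt in 7.4, 7.5 or 12.1.
- *DLT.* A related event that needed no treatment is a DLT under the definition in Protocol 7.4 and is not one under the later sentence in that section.
- *Grades.* Grade 3 in Protocol 7.4 refers to being unable to carry on normal activities and to needing professional medical attention. Protocol 7.5, Protocol 8.1 and SAP 6.6.2 share another scale, based on medical significance, hospitalization, disability or limits on self-care. The same event could be graded differently on the two.

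**The case against.** The strongest reply is that SAP section 2 only restates the protocol, that MTD is not an objective, and that the trial did have a toxicity gate. Much of this stands.

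- **Toxicity and escalation.** A reader might infer that toxicity counts play no part in escalation. The documents do not support that. Dosing Cohort 2 requires enrolment, and one related Grade 3+ event halts enrolment until review, so it blocks escalation meanwhile. Only expansion and the declaration of an MTD lack a visible rule.
- **Redaction.** A reader might infer that the plan has no such rule. The redactions lie where it would stand, so only its visibility can be judged. An expansion rule found there would still have to be squared with N = 7.
- **DLT definition.** The later sentence in Protocol 7.4 can be read as narrowing the definition to events both related and needing treatment. That is possible, but the text does not say so.
- **Grades.** Protocol 7.5 writes the Protocol 8.1 scale into the halting rule and the SAP uses the same scale, so SAP grading is determinate. Protocol 7.4 is the section that differs.
- **Existing outputs.** The SAP lists all adverse events and tabulates related events and maximum grade by cohort. With three subjects in each bilateral cohort, related Grade 3+ events should be readable from the listing. DLTs under either wording are not tabulated.
- **Intervals.** A reader might infer from the wide intervals that three subjects can never yield an MTD. That does not follow: a count-based MTD is set by its rule, not by interval width.

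**Conclusion.** The point holds in limited form. The mismatch between the label and the fixed 1 + 3 + 3 stands in visible text. It rests on reading three-six as three expandable to six; on that reading any expansion needs at least 9 or 10 subjects, depending on whether Cohort 1A counts, against 7. The absence of an expansion rule and an MTD rule is a matter of what is visible, not proven.

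The differences in stopping criteria, DLT wording and grade scale are visible and do not depend on the redactions. This review does not say which wording is right.

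It might seem natural to have the SAP now choose one DLT definition and report that count. The documents do not support this. The SAP is dated April 2022 and Protocol 11.6.3 planned enrolment to end in December 2017, so if those dates held, the choice would be made after dosing in an uncontrolled study. What is left to protect is how the results are described.

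**What to change.** 1. **SAP 2.2.** If a redacted passage gives an expansion and MTD rule, cite it and reconcile it with N = 7. Otherwise remove the three-six label and the stated MTD purpose, note the departure from Protocol 2.0 and 6.3, and state that the study describes safety at two dose levels in fixed cohorts and will draw no MTD conclusion.
2. **Reconciliation by the sponsor.** Three sets of passages must be brought into line: the stopping criteria (Protocol 6.6 with 7.4, 7.5 and 12.1), the two DLT wordings within Protocol 7.4, and the grade scales (Protocol 7.4 with 7.5, 8.1 and SAP 6.6.2).
3. **Reporting, if DLTs are reported.** Give subjects with a DLT over n for Cohorts 1B and 2 separately, under each documented wording, labelled post hoc. List the Cohort 1A subject individually, because only one limb was to be treated. Any statement that a dose was tolerated should note that 0/3 is compatible with a rate of up to 70.8% (exact two-sided 95%).

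The cost is a wording change, a reconciliation note and one small table. Enrolment and conduct are unchanged. The downside is a less favourable stated claim.
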